6.0 DATA MANAGEMENT CONSIDERATIONS

6.1 Data management

The study members will be present at all times during the procedures, and will adhere to the standard methods of care and safety of the participating subjects. Patient information will subsequently be accessed by only those investigators involved in the study who have been named on this protocol. Data will be recorded electronically. Research data resulting from the analysis of will be safeguarded in password-secured laboratory computers where

careful records will be maintained, and data-backup will be performed routinely. Medical information acquired from subjects directly will be de-identified and stored in a secure location in the research office.

APPENDIX A: Participant Eligibility Checklist

Protocol Title:	The Effect of Pneumatic Tourniquet Use on Upper Extremity Edema Following Axillary Lymph Node Dissection
Protocol Number:	BRS0075
Principal Investigator:	[name]

II. Subject Information:

Subject Name/ID:
Gender:  Male  Female

III. Study Information:

SRC Approved IRB Approved Contract signed

IV. Inclusion/Exclusion Criteria

Inclusion Criteria (From IRB approved protocol)	Yes	No	Supporting Documentation*
1. 18 years of age or earlier			
2. Presence of prior axillary lymph node dissection (group A)			
3. Absence of prior axillary lymph node dissection (group B)			
Exclusion Criteria (From IRB approved protocol)			
1. New-onset lymphedema of the involved limb			
2. Infection including cellulitis			
3. Trauma or planned axillary surgery within 6 months of participation.			

*All subject files must include supporting documentation to confirm subject eligibility.

The method of confirmation can include, but is not limited to, laboratory test results, radiology test results, subject self-report, and medical record review.

IV. Statement of Eligibility

By signing this form of this trial I verify that this subject is [**eligible** / **ineligible**] for participation in the study. This study is approved by the Stanford Cancer Institute Scientific Review Committee, the Stanford IRB, and has finalized financial and contractual agreements as required by Stanford School of Medicine's Research Management Group.

Treating Physician Signature:	Date:
Printed Name:	

Secondary Reviewer Signature:	Date:
Printed Name:	

Study Coordinator Signature:	Date:
Printed Name:

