3.0 STUDY ENROLLMENT AND PARTICIPANT ELIGIBILITY

All patients over the age of 18 who have previously undergone axillary lymph node dissection will be invited to participate in the study. Participants will be identified via chart review of patients with prior ALND.

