3.1 Study Enrollment

Recruitment will occur via telephone or in-person encounters based on retrospective review for patients meeting the above inclusion criteria. Advertising for this study is not planned. Participants will be screened based on the above criteria and the exclusion criteria in part 3.2 below. Participants who fail inclusion on screening will be excluded.

The study coordinator or the above study members will consent the patient prior to involvement. In a closed and quiet room, the potential research subject will be able to ask any questions regarding the study and its procedures. No recruitment materials will be provided at the time of consent. Participants may withdraw consent at any time.

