3.2 Participant Criteria

All patients over the age of 18 who have previously undergone axillary lymph node dissection will be invited to participate in the study. Patients will serve as their own internal control, using both arms which are ipsilateral and contralateral to the side of ALND. Patients will be excluded who have new-onset lymphedema of the involved limb, infection including cellulitis, or trauma or planned axillary surgery within 6 months of participation.

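### Two inclusion items on the Appendix A eligibility checklist contradict Sections 3.0 and 3.2: item 1 reverses the age criterion, and item 3 lists absence of prior ALND

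*Combined protocol and SAP*

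**What the plan says.** **Body of the protocol.** Section 3.0 states: "All patients over the age of 18 who have previously undergone axillary lymph node dissection will be invited to participate in the study". Section 3.2 repeats the sentence and adds the control arrangement: "Patients will serve as their own internal control, using both arms which are ipsilateral and contralateral to the side of ALND". Section 3.0 also says that participants are found by reviewing the charts of patients with prior ALND. Section 3.1 adds: "Participants who fail inclusion on screening will be excluded".

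**Appendix A, Participant Eligibility Checklist.** The table heading attributes the criteria to the IRB-approved protocol. There are three inclusion items, each with its own Yes and No box:

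- Item 1: "18 years of age or earlier"
- Item 2: "Presence of prior axillary lymph node dissection (group A" (closing bracket omitted here)
- Item 3: "Absence of prior axillary lymph node dissection (group B" (closing bracket omitted here)

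The three exclusion items agree with Section 3.2. A footnote says: "All subject files must include supporting documentation to confirm subject eligibility". The statement of eligibility begins "By signing this form of this trial I verify that this subject is", followed by a choice of eligible or ineligible, with signature lines for the treating physician, a secondary reviewer and the study coordinator.

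**The concern.** A checklist that claims to reproduce the protocol's criteria should reproduce them. This one departs from them twice, on the form where eligibility is certified.

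The age item points in the opposite direction from the body. Someone completing it as worded would mark the intended adults as failing an inclusion criterion, and Section 3.1 excludes those who fail inclusion.

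Item 3 does not belong to the design described elsewhere. The study has no comparison group of people without ALND; the comparison is between two arms of the same patient. If items 2 and 3 are taken as alternative routes into the study, the checklist no longer screens on ALND history, which is the defining feature of the study population.

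What is at stake is the agreement between the eligibility form and the protocol. The sample size and the analysis method do not depend on it.

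**Working it through.** No figure in the plan bears on this point, so the check is a side-by-side reading of the criteria.

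**Step 1: age.**

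| Source | Admitted ages |
|---|---|
| Sections 3.0 and 3.2, strict reading | above 18 |
| Sections 3.0 and 3.2, loose reading | 18 and above |
| Appendix A, item 1 | 18 and below |

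On the strict reading the body and the form share no age. On the loose reading they share only age 18. On either reading, every patient aged 19 or more is eligible under Section 3.2 and a No on item 1.

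**Step 2: what items 2 and 3 could mean.** The form has no instruction linking them, and the group A and group B labels are not defined in any section. There are three possible readings.

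- *Alternatives.* A subject needs a Yes on item 2 or on item 3. Everyone either has or has not had ALND, so everyone satisfies the pair and the pair screens nobody out. This conflicts with Sections 3.0 and 3.2.
- *Two arms of one patient.* Item 2 would describe the operated side and item 3 the other side. This fits the within-patient design, and Section 5.3 does use the word group for sets of extremities. But the form certifies a subject, not an arm, and does not state this reading.
- *Both required of the same subject.* Nobody can satisfy this. The group labels make it an unlikely intention, and nothing below relies on it.

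**Step 3: two example adults over 18, with items 2 and 3 read as alternatives.**

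| | Item 1 as worded | Item 2 | Item 3 | Passes form as worded | Passes form if only item 1 is aligned with Section 3.2 | Eligible under Section 3.2 |
|---|---|---|---|---|---|---|
| Adult with prior ALND | No | Yes | No | No | Yes | Yes |
| Adult without ALND | No | No | Yes | No | Yes | No |

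As worded, the form rejects the intended adult because of item 1. If only item 1 is aligned, the form accepts the intended adult but also accepts an adult without ALND, so item 3 needs attention in its own right.

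**Step 4: why a person without ALND does not fit.** The primary comparison in Sections 5.0 and 5.2 is paired: percentage change in hand volume in the arm on the ALND side against the other arm of the same patient. Without ALND neither arm is ipsilateral, so that within-patient difference is not defined.

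**Step 5: link to the sample size.** Section 5.3 rests on 45 patients with two arms each, a standard deviation of 1.6 percentage points and a margin of 1 percentage point. None of these comes from Appendix A, so the checklist wording does not change the power calculation.

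**The case against.** The strongest reply is that the intent is plain. The body gives the criterion twice in the same words, recruitment starts from charts of patients with prior ALND, and item 1 is probably a slip for its opposite. The group labels suggest that items 2 and 3 were never meant to apply jointly. The form also has a supporting-documentation column, names medical record review as one acceptable source, and has three signature lines, so a mistake at screening could be caught.

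Most of this stands, and it keeps the point minor. It also rules out several stronger inferences:

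- A reader might infer that none of the 45 planned participants can meet items 2 and 3 together, so the form is impossible to complete. That needs the joint reading, which the group labels make strained.
- A reader might infer that a signed form cannot show that Section 3.2 was applied. The documents do not support this: age and ALND history could be confirmed from the supporting documentation despite the wording.
- A reader might infer that minors or people without ALND were or will be enrolled, or that the result will be biased. Nothing in the documents shows this.

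The reply does not remove the contradiction. Supporting documents can rescue a misworded item, but they do not make it agree with the protocol it claims to quote. And the likely explanation for item 1 does not cover item 3, which is not a one-word slip.

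**Conclusion.** The point holds as a minor but real inconsistency in an operative form. Item 1 reverses the age criterion of Sections 3.0 and 3.2. The overlap is empty, or age 18 alone, depending on whether over 18 is taken strictly, so as worded the item fails essentially every intended adult. Item 3 names absence of ALND as an inclusion criterion in a study that recruits only patients with ALND; read as an alternative to item 2, it would admit people who cannot contribute to the paired comparison. If the labels were meant as the two arms of one patient, the fault is one of wording, but the form still does not say so.

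The conclusion assumes that the checklist is used as printed and that its items mean what they say. It does not depend on how anyone has actually been screened, which the documents do not report. There is no effect on the power calculation.

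**What to change.** In Appendix A:

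1. Reconcile item 1 with the age criterion in Sections 3.0 and 3.2, so that the form and the protocol state the same rule.
2. Remove item 3 and the group A and group B labels. If they were meant as the two arms of one patient, reword them to say so.
3. Re-confirm eligibility, from the supporting documentation, for any subject whose form has already been signed with the present wording.

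The cost is a short wording change, submitted as a modification and approved by the IRB before use, as the section on protocol review and amendments requires, plus the time to re-check any signed forms. No endpoint, procedure, sample size or analysis changes.
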